5. DATA HANDLING

5.1. **Computing Environment**

All descriptive statistical analyses will be performed using SAS statistical software (Version 9.4 OR HIGHER), unless otherwise noted. Medical History and adverse events will be coded using MedDRA available version. Concomitant medications will be coded using World Health Organization (WHO) Drug Dictionary available version.

5.2. Data Conventions

5.2.1. Last extension treatment administration date, End of extension Study date and Period definitions

The last extension treatment administration date will be defined as the date from the treatment termination reported in the extension period eCRF page. If this date is missing, the last date with a drug intake in the eDiary that is inferior or equal to Month 12 visit or the last available date with a drug intake in the eDiary if the subject discontinued the extension treatment will be used.

For subjects who entered the extension, the end of the extension study date will be the last assessment date in the extension study defined as last assessment recorded in the eCRF (excluding end date of adverse events and concomitant medications) or ediary date (excluding drug intakes recorded after last extension treatment administration date). This will not necessarily be the same date as last assessment date as recorded in the eCRF.

For each 28-day period prior to Month X (except Month 12), the end of the period will be defined as the Month X visit date. If subject discontinued prior to Month X, the end of the period will be the date from the treatment termination of extension period eCRF page or the last date with a drug intake in the eDiary if missing. If the subject missed the Month X visit (but did not discontinue), the subject might still have filled the diary during that time: the theoretical Month X date will be used to define the end of the 28-day period. The theoretical Month X is defined with respect to Day 1 as Month X= Day 1+ $28^{*}X$.

For the 28-day period prior to Month 12, the end of the period will be defined as the last extension treatment administration date.

Note:

For Adverse Events, Concomitant Medications and Daily diaries data collected on the Month 6 date will be part of the extension for subjects entering the extension study.

For Adverse Events, Concomitant Medications and Daily diaries, data collected on the Month 12 date will be part of the Extension Follow-up period for subjects entering the Extension follow-up period.

The extension treatment period will be defined as Month 6 up to (Month 12 date -1) or treatment discontinuation date.

The extension follow-up period will be defined as the Month 12 date or (treatment discontinuation date+1) up to the extension follow-up end date (for subjects who entered the extension follow-up).

5.3. Methods of Pooling Data

Not Applicable

5.4. Withdrawals, Dropouts, Loss to Follow-up

In general, there will be no substitutions made to accommodate missing data points due to withdrawals, dropouts and loss to follow-up. All data recorded in the CRF will be included in data listings that will accompany the clinical study report.

In case of early discontinuation, the subject was to be instructed to complete the relevant eDiary questionnaires as soon as possible upon treatment discontinuation.

Withdrawal during treatment period:

Subjects discontinuing participation in the study during the Extension Treatment Period were to undergo the procedures required at Month 12, except the DXA in case of discontinuation before Month 9 visit. These subjects were to enter the 6-month Extension Follow-Up Period and were to continue daily eDiary recording for 6 months and up to the Month 6 ExFU visit in order to continue to collect efficacy and safety data.

PK sampling was not required if the subject had no IMP administration the day prior to the withdrawal visit.

Withdrawal during follow-up period:

Subjects discontinuing participation in the study during the Extension Follow-Up Period were to undergo the procedures required at the Month 6 ExFU visit, which included completion of all ClinRO and ePRO questionnaires, except for DXA scans in subjects who discontinued before the Month 3 ExFU visit.

5.5. Visit Windows

For all analyses except for the DXA assessments and the diary questionnaires, the visits as collected in the eCRF will be used.

The rules for visit day calculations are listed in Table 1 below.

E-diary questionnaires:

For diary questionnaires (EHP-30, EQ-5D-5L, HRPQ, HRUQ, PGIC, PPGIC, PGIS, PROMIS, SSIQ) except for the PSIQ, the e-diary dates of assessment of each visit will be checked versus the dates of same visit in eCRF to handle for e-diary visit errors. Only assessments within the window of the date of eCRF+/-14 days will be used in analyses. In case of multiple assessments falling within the same window of an eCRF date, the non-empty record with completion date closest to the eCRF date will be used.

Due to the war situation in Ukraine, some subjects from Ukraine sites may have completed visits and e-diary questionnaires but not collected the data in the eCRF. For all ediary questionnaires data of subjects from Ukraine sites with a later questionnaire date of 24FEB2022, the e-diary dates will be compared to theoretical visits dates instead of eCRF visits dates if eCRF dates are missing.

For data from discontinued visits, the discontinuation visit date should be compared to theoretical visit dates. Only assessments within the window of theoretical date +/-14 days will be used for analyses, if it is planned to have a such assessment at this visit and no other assessment is in the window. If a subject discontinued in the extension treatment period, date will be compared to the theoretical visit dates in the extension treatment period as described in Table 1. If a subject discontinued in the extension follow-up period, date will be compared to the theoretical number of the theoretical visit dates in the extension follow-up period, date will be compared to the theoretical number of the theoretical visit dates in the extension follow-up period, date will be compared to the theoretical number of the theoretical visit dates in the extension follow-up period, date will be compared to the theoretical visit dates in the extension follow-up period, date will be compared to the theoretical visit dates in the extension follow-up period, date will be compared to the theoretical visit dates in the extension follow-up period, date will be compared to the theoretical visit dates in extension follow-up period from Table 2.

Note that assessments from discontinued visits in **Example** eDiary device are entered under Month 12 (Month 6 Extension FU in follow-up). They will be recoded as discontinued visits before applying the windowing rules.

Pharmacokinetics data

Visit windows rules for PK data will be the following:

- PK assessments will be included in analysis if:
 - Assessment is Pre-dose (or PK time = dose time), or IMP intake is not done on the day of PK sampling (i.e. considered as pre-dose), and,
 - PK assessment date is within +/-10 days of the theoretical visit and up to 2 days after last IMP intake for Month 12 visit.

If the PK sampling time is missing, or the IMP intake on the same day is done and the IMP intake time is missing then assessments will not be included.

IMP intake status (done/not done) and IMP intake time from the Pharmacokinetics eCRF page will be used.

PK samples analysed after the period of long term stability will be excluded.

DXA data

Visit windows rules for DXA assessments will be the following:

- The DXA assessment at Month 9 will be derived as the first non-missing DXA assessment with acceptable quality (accepted="Yes") and dated between Month 9 theoretical date (=Day 253) -28 days and Month 9 theoretical date + 28 days.
- The DXA assessment at Month 12 will be derived as the first non-missing DXA assessment with acceptable quality (accepted="Yes") and dated between Month 12 theoretical date (=Day 337 in the main study) -28 days and Month 12 theoretical date + 28 days.
- The DXA assessment at Month 6 Extension Follow-Up will be derived in the same way as the DXA assessment at Month 12. Theoretical date of Month 6 Extension Follow-up is 168 days after Month 12 theoretical date or after treatment discontinuation.

Other safety data:

For other safety data, data from early discontinuation should be compared to theoretical visits dates. Only assessments within the window of theoretical date +/-14 days will be used for analyses, if it is planned to have a such assessment at this visit and no other assessment is in the window. If a subject discontinued in the extension treatment period, date will be compared to the theoretical visit dates in extension treatment period as described in Table 1. If a subject discontinued in the extension follow-up period, date will be compared to the theoretical visit dates in extension follow-up period, date will be compared to the theoretical visit dates in extension follow-up period, date will be compared to the theoretical visit dates in extension Follow-up period from Table 2.

For unscheduled safety assessments, if the assessment occurs within a window of theoretical date +/- 14 days for a planned eCRF visit for which it was planned per protocol to have such assessment, and no assessment was done for that visit, the assessment will be assigned to that visit. If the assessment is equally distant from two eCRF visits with no corresponding safety assessment, the assessment will be assigned to the next visit.

For biopsy, DXA assessment or laboratory assessment, if an assessment has been assigned in external data to a follow-up visit of the main study for subjects who entered in the extension study, the visit of assessment should be reassigned with the same rules described above for unscheduled safety assessment.

Visit	Theoretical Date
Month 6	Day 169
Month 7	Day 197

Table 1 Theoretical Visit Dates in Extension Treatment Period

CRS-BS-TP-000005 V 2.0

Page 29 of 99

Kissei / Cytel Confidential: This is a controlled document and shall not be changed, saved, copied or reproduced by any unauthorized person.

Month 8	Day 225
Month 9	Day 253
Month 10	Day 281
Month 11	Day 309
Month 12	Day 337

Table 2 Theoretical Visit Dates in Extension Follow-up Period

Visit	Theoretical Date
Month 1 ExFU	Month 12 or treatment discontinuation date + 28
Month 3 ExFU	Month 12 date or treatment discontinuation date + 84
Month 6 ExFU	Month 12 date or treatment discontinuation date + 168

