5.5.1 Pharmacokinetics/Pharmacodynamics

Linzagolix was evaluated in a Phase 1 single/repeated-dose study (Study KLH1101) in which Japanese and Caucasian pre- and post-menopausal women received single doses of linzagolix from 12.5 to 700 mg and repeated once daily doses of 100 to 400 mg once daily for 7 days under fed and fasted conditions. Linzagolix was safe and well-tolerated, showed linear PK, a half-life of about 15–20 hours, and little difference between pre- and post-menopausal women or between Japanese and Caucasian women. There was a dose-dependent suppression of E2, LH and follicle-stimulating hormone (FSH).

Study 17-OBE2109-001 evaluated the tolerability and PK of a single supra-therapeutic dose of 700 mg linzagolix, and effects of therapeutic and suprathreshold doses of linzagolix on the QTc interval (QT interval corrected for heart rate). Subjects received a 200 mg dose of linzagolix (therapeutic target exposure), a 700 mg dose of linzagolix (suprathreshold target exposure), a 400 mg dose of moxifloxacin (positive control), and placebo with an appropriate washout. Linzagolix at 700 mg was well tolerated. A borderline effect of linzagolix on the QTc interval was identified with prolongations exceeding the threshold of concern by less than 2 msec. The categorical data for QTc showed no values greater than 480 msec and no changes greater than 30 msec following administration of the suprathreshold and therapeutic doses. Thus, based on the magnitude of the QTc prolongation, the observed effects are not considered to be clinically significant.

The open-label study, KLH1103, assessed the absorption, metabolism, and excretion of linzagolix in 6 women of non-childbearing potential. Linzagolix was the predominant component in plasma and all plasma metabolites were present at less than 10% of the total drug related exposure. Similarly, unchanged linzagolix was also a major component in urine and feces. Linzagolix was eliminated in urine (52%) and, to a lesser extent, in feces (38%).

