10.2.1 Treatment Period

During the entire Treatment Period:

- the subject will use the same eDiary as during the main study. The eDiary should be completed daily, in the evening at approximately the same time, for use of provided/prescribed analgesics, uterine bleeding, pelvic pain, dyspareunia, dyschezia and daily function.
- the subject will take her daily dose of study medication at home except on the day of study visits where she will take her daily dose at site. There will be no IMP intake at the Month 12 visit. The last dose of study medication in this extension study will be the dose taken the day before Month 12 visit.
- the subject will be asked to bring her eDiary and her IMP kits at each visit to the site.
- the subject will receive contraception counselling at each visit.
- the subject will be provided/prescribed a limited quantity (as per Investigator's judgement) of standard doses of permitted analgesics as rescue medication for EAP for the duration of the study.
- the subject will receive calcium 500 to 1000 mg and vitamin D 400 IU supplementation which she will be advised to take daily (at least 4 hours from the intake of the study drug) until the end of the study. Intake should be recorded at each study visit in eCRF.
- AEs and concomitant medications will be recorded in the eCRF (excluding any provided/prescribed analgesics used for EAP will be recorded daily in the eDiary only).

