10.5 LINZAGOLIX AND KP017 PLASMA LEVELS

PK blood samples will be collected from each subject at each study visit during the Treatment Period for determining linzagolix and KP017 plasma levels.

At the visits where IMP intake is at site, i.e. at Months 6, 7, 8, 9, 10 and 11 visits, PK sampling will be performed before IMP intake. The approximate time of dose administration on the four previous days and time of PK sampling will be recorded in the eCRF.

In case of early discontinuation visit, PK sampling is not required at the withdrawal visit if the subject had no IMP administration the day prior to the withdrawal visit.

Details of the blood sampling process, sample handling and shipment are described separately in a laboratory manual provided by the central laboratory.

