For descriptive statistics of plasma concentrations mean (arithmetic and geometric), standard deviation, median, 1st and 3rd quartiles, minimum, maximum, coefficient of variation (CV%) and number of observations will be provided. Concentrations below the limit of quantification (LOQ) will be assigned a value of zero. Missing values will not be imputed, and if sufficient data are missing for a given subject, that subject may be considered non-evaluable for pharmacokinetic analysis and would not be included in the PK Set.

All plasma concentration data will be displayed in listings. PK assessment day and time, IMP intake status and IMP intake time on the day of PK assessment and on the previous days will be included in the listings.

Explorative analyses of correlations between plasma concentrations and intrinsic PK factors such as body weight/BMI, race, age will be performed, as appropriate, and will be reported separately.

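### SAP 5.5 limits time since last intake for PK samples only at Month 12, so samples 72 h or more after a dose enter the Month 6-11 summaries

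*SAP*

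**What the plan says.** SAP 5.5 (Visit Windows, pharmacokinetics data) sets two conditions for including a sample. First, it must be pre-dose, or fall on a day with no dose: "IMP intake is not done on the day of PK sampling (i.e. considered as pre-dose". Second, the date must fit: "PK assessment date is within +/-10 days of the theoretical visit and up to 2 days after last IMP intake for Month 12 visit". As written, the 2-day clause belongs to Month 12 only.

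The other sample-level exclusions in 5.5 concern missing times ("If the PK sampling time is missing, or the IMP intake on the same day is done and the IMP intake time is missing") and samples analysed beyond their long-term stability period. Neither deals with time since the last dose.

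Protocol 10.5 describes the planned sampling: "at Months 6, 7, 8, 9, 10 and 11 visits, PK sampling will be performed before IMP intake". Month 12 differs. Protocol 10.2.1 says "There will be no IMP intake at the Month 12 visit" and places the last dose on the day before.

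The data needed for a time-since-dose rule are collected. Protocol 10.5: "The approximate time of dose administration on the four previous days and time of PK sampling will be recorded in the eCRF". SAP 6.5 uses them for display only: "IMP intake status and IMP intake time on the day of PK assessment and on the previous days will be included in the listings".

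SAP 6.5 plans arithmetic and geometric means of plasma concentrations and sets values below LOQ to zero. SAP 3.2 classes the PK analyses as exploratory. Protocol 13.4 leaves rules for excluding individual data points to the SAP.

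**The concern.** Neither route to inclusion looks back at when the previous dose was taken. A woman who missed several doses and then took her tablet at the site after sampling qualifies as pre-dose. So does a woman who took nothing that day because treatment was interrupted. Interruptions are foreseen: the serum calcium rule in Protocol 10.7.2.1 provides for one, and drug interruption is a recorded action in Protocol 12.1.1.

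The Month 12 clause shows that the SAP itself regards samples more than 2 days after the last intake as unsuitable for the summary. Leaving the clause out at Months 6-11 means that the same sample is kept at one visit and dropped at another. At stake is whether the visit-by-visit concentration table describes women on drug in the same way throughout.

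**Working it through.** The plan states no figure on this point, so there is nothing to reproduce first.

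**Step 1. Which samples are treated differently?** Count by calendar day, with once-daily dosing.

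| Days since last intake | Doses missed | Approx. hours | Months 6-11 | Month 12 |
|---|---|---|---|---|
| 1 | 0 | 24 | kept | kept |
| 2 | 1 | 48 | kept | kept |
| 3 | 2 | 72 | kept | excluded |
| 4 or more | 3 or more | 96 or more | kept | excluded |

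The rules diverge only from about 72 h.

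**Step 2. How low is such a sample?** The input is the linzagolix half-life in Protocol 5.5.1: "a half-life of about 15–20 hours". Assume mono-exponential decline after 24 h. The fraction of the 24 h pre-dose level is f = 2^(-extra hours / half-life).

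- 72 h (48 extra hours): 2^(-48/15) = 0.109; 2^(-48/20) = 0.19. That is 11-19%.
- 96 h (72 extra hours): 0.036 to 0.083, or 4-8%.
- 192 h (seven missed doses): 0.0004 to 0.003, well under 1%.

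The documents give no half-life for the metabolite KP017, so these figures apply to linzagolix only.

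**Step 3. What happens to a visit summary?** Let s be the share of samples affected. The documents do not give s; 5% and 10% are assumptions. The arithmetic mean falls by s(1 - f) and the geometric mean by 1 - f^s. For 72 h samples:

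| s | Half-life | Fall in arithmetic mean | Fall in geometric mean |
|---|---|---|---|
| 5% | 15 h | 0.05 × 0.891 = 4.5% | 1 - 0.109^0.05 = 10.5% |
| 5% | 20 h | 0.05 × 0.81 = 4.1% | 1 - 0.19^0.05 = 8.0% |
| 10% | 15 h | 0.10 × 0.891 = 8.9% | 1 - 0.109^0.10 = 19.9% |
| 10% | 20 h | 0.10 × 0.81 = 8.1% | 1 - 0.19^0.10 = 15.3% |

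The ranges are about 4-9% (arithmetic) and 8-20% (geometric). At s = 2% they are 1.6-1.8% and 3.3-4.3%.

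**Step 4. Values below LOQ.** A single zero makes a geometric mean zero or, on the log scale, undefined. The LOQ is not stated, so the documents do not show how long a gap would be needed to reach it. Long gaps are one route to such a value in a woman still attending on-treatment visits.

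**Step 5. Do other rules remove these samples?** The Extension PK Set (SAP 4.1) drops whole subjects with major deviations affecting PK, but no missed-dose or interruption criterion is given. The only compliance example in the SAP, below 60% in 4.2, concerns the Per Protocol efficacy set. Protocol 10.7.2 waives PK sampling at a withdrawal visit when no dose was taken the day before. That does not reach Months 6-11 visits of women who remain in the study, nor does it exclude a sample that was taken.

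**The case against.** The strongest defence is that the two situations differ. Month 12 is the one scheduled visit without dosing at the site, and a window of ±10 days there could capture samples taken after treatment had ended. At the earlier visits the woman is on treatment and takes her tablet at the visit. Women who stop treatment leave that schedule. This explains why the clause was written for Month 12. It does not explain why a sample 3 or more days after the last intake should count earlier, when the gap arises from missed doses or an interruption.

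It is also fair to say that the SAP promises pre-dose concentrations, not steady-state 24 h troughs, and that summarizing what was observed under actual adherence is a legitimate descriptive choice. But the SAP does not make that choice consistently, since Month 12 departs from it. The listings let a reader find affected samples, but they do not change the summary.

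A reader might infer several stronger points that the documents do not support:

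- *That a single missed dose makes the visits incomparable.* Month 12 also accepts a sample 2 days after the last intake, so that case is handled alike everywhere.
- *That the net bias is downward.* There is no lower limit on time since dose. A sample 12 h after an evening dose would read about 1.5-1.7 times the 24 h level. Missed doses act only downward, but the net direction over all samples is not fixed.
- *That the correlations with weight, race and age will reflect adherence.* They are exploratory and reported separately, and the documents do not show whether they will use this filter or the actual dose times.
- *That only samples close to 24 h should be kept.* No such window has a basis in the documents. Home dosing has no fixed clock time and prior dose times are approximate, so a narrow window could discard valid pre-dose samples from evening dosers.

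**Conclusion.** The point holds in a limited form. The inclusion rule in SAP 5.5 admits samples at Months 6-11 that it would exclude at Month 12, and no other stated rule reliably removes them. For 72 h samples the possible size is about 4-9% on the arithmetic mean and 8-20% on the geometric mean. This assumes that 5-10% of samples are affected, a half-life of 15-20 h and mono-exponential decline. With few such samples the arithmetic mean would barely move; longer gaps would lower the geometric mean further. The consequence is confined to exploratory concentration summaries and anything built directly on them. No efficacy or safety conclusion depends on it. It is worth correcting because the correction is nearly free.

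**What to change.** In SAP 5.5, apply the existing limit of up to 2 days after the last IMP intake at every on-treatment visit, Months 6 to 12. For Months 6-11, define last intake as the most recent one before the sample, so that a dose taken at the site afterwards does not count. The dose times recorded for the four previous days are enough: keep the sample if the latest recorded dose was 1 or 2 days earlier, and exclude it if the latest was 3 or 4 days earlier or if none was taken in those four days. State how a blank record is handled. List the excluded samples with the reason.

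The cost is one sentence and one programming filter. Probably a few samples would move from the summary to a listing; the actual number is not known from the documents. The limit removes one source of values below LOQ but does not settle how the geometric mean treats zeros.
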